†††† AESIs will be collected throughout the trial as SAEs to ensure that the events are communicated to the Sponsor in an expedited manner and followed up until the end of the follow-up period or resolution, as per the assigned causality.

Table of Study Procedures - Group 2

Phase III Trial, 5 Visits, 4 Vaccination Visits, 4 Telephone Calls, 1 or 3 Blood Samples, 11- to 12-Month Duration per Subject

Visit	Visit 1	Telephone Call (TC) 1*	Visit 2	TC2*	Visit 3	TC3*	Visit 4†	TC4*	Visit 5‡
Approximate age of subjects	2 months	-	3 months	-	4 months		12-13 months	-	13-14 months
Trial timelines (days)	Day 0	Visit 1 + 8 days	Visit 1 + 30 days	Visit 2 + 8 days	Visit 2 + 30 days	Visit 3 + 8 days	-	Visit 4 + 8 days	Visit 4 + 30 days
Time windows (days)	-		+14 days		+14 days				+21 days
Informed consent	X								
Inclusion/exclusion criteria	X								
Collection of demographic data	X								
Medical history (including maternal prenatal pertussis vaccination)	X								
Physical examination §	X						X**		
Measurement of temperature††	X		X		X		X		
Contact IRT system for randomization, allocation of subject number, and vaccine assignment	X								
Contact IRT system for vaccine assignment			X		X		X		
Review of temporary contraindications for blood sampling‡‡			X		X				X
Blood sampling (BL)§§			BL1 (3 mL)***		BL2 (3 mL)***				BL3 (6 mL)
					BL1 (3 mL)†††		BL2 (3 mL)†††		
Review of warning and precautions to vaccinations	X		X		X		X		
Review of contraindications to subsequent vaccinations and conditions for withdrawal‡‡‡			X		X		X		
Vaccination with MenACYW conjugate vaccine			X				X		
Vaccination with Bexsero®	X				X				

Visit	Visit 1	Telephone Call (TC) 1*	Visit 2	TC2*	Visit 3	TC3*	Visit 4†	TC4*	Visit 5‡
Approximate age of subjects	2 months	-	3 months	-	4 months		12-13 months	-	13-14 months
Trial timelines (days)	Day 0	Visit 1 + 8 days	Visit 1 + 30 days	Visit 2 + 8 days	Visit 2 + 30 days	Visit 3 + 8 days	-	Visit 4 + 8 days	Visit 4 + 30 days
Time windows (days)	-		+14 days		+14 days				+21 days
Vaccination with routine pediatric vaccines§§§	X		X		X				
Immediate surveillance (30 minutes) and recording of any immediate unsolicited AEs	X		X		X		X		
Diary card (DC) provided****	DC		DC		DC		DC		
Telephone call		X		X		X		X	
Diary card reviewed and collected			DC		DC		DC		DC
Recording of solicited injection site & systemic reactions	X		X		X		X		
Recording of unsolicited AEs	From Day0 to Day30 after each vaccination								
Reporting of serious adverse events (SAEs, including AESIs)††††	To be reported throughout the trial								
Collection of reportable concomitant medications	X		X		X		X		X
Trial termination record									X

Note: Each visit may be conducted at the site (site visit) or at the subject's home (home visit).

* This call is made 8 days after the respective vaccinations. If day 8 falls on a weekend or holiday, the telephone call may be made on the following business day. During this telephone call, the staff will find out whether the subject experienced any SAE not yet reported and will remind the subject's parent / legally acceptable representative to continue using the diary card, and confirm the date and time of the next visit.

† Visit 4 may occur anytime from the day the subject becomes 12 months of age until the day before becoming 14 months of age.

‡ Routine pediatric vaccines may be given as per standard of care outside of the study, after all visit procedures have been completed. The 3rd dose of Bexsero[®] will be provided by the Sponsor to complete the vaccination series.

§ Physical examination should be performed as per standard of care.

** A health assessment will be performed by a study nurse at Visit 4. A physical examination may be performed on the basis of relevant medical history/study nurse health assessment according to the investigator's clinical judgment.

†† Temperature (route as per standard of care) needs to be measured before each vaccination and recorded in the source documents.

‡‡ Should a subject receive oral or injectable antibiotic therapy within 3 days prior to any blood draw, the investigator will postpone that blood draw until it has been 3 days since the subject last received oral or injectable antibiotic therapy. Postponement must still be within the timeframe for blood draw. If postponement would result in the sample collection falling outside of this timeframe, the blood sample should be collected without postponement, and it should be documented appropriately that the sample was taken less than 3 days after stopping antibiotic treatment.

§§ Blood sample will be drawn prior to vaccination.

*** Blood samples will be drawn from ~70 randomized subjects only (Subset A).

††† Blood samples will be drawn from ~ 90 randomized subjects only (Subset B).

‡‡‡ A physical examination may be performed on the basis of relevant medical history at the time of the visit according to the investigator's clinical judgment.

§§§ Routine pediatric vaccines: At Visit 1: Infanrix hexa[®], Rotarix[®], Prevenar 13[®]; at Visit 2: Infanrix hexa[®], Rotarix[®]; at Visit 3: Infanrix hexa[®], Prevenar 13[®]

**** The diary card dispensed to the subject's parent/legally acceptable representative at each visit must correspond to the number of injections given at that visit.

†††† AESIs will be collected throughout the trial as SAEs to ensure that the events are communicated to the Sponsor in an expedited manner and followed up until the end of the follow-up period or resolution, as per the assigned causality.

Table of Study Procedures - Group 3

Phase III Trial, 5 Visits, 4 Vaccination Visits, 4 Telephone Calls, 3 Blood Samples, 11- to 12-Month Duration per Subject

Visit	Visit 1	Telephone Call (TC) 1*	Visit 2	TC2*	Visit 3	TC3*	Visit 4†	TC4*	Visit 5‡
Approximate age of subjects	2 months	-	3 months	-	4 months		12-13 months	-	13-14 months
Trial timelines (days)	Day 0	Visit 1 + 8 days	Visit 1 + 30 days	Visit 2 + 8 days	Visit 2 + 30 days	Visit 3 + 8 days	-	Visit 4 + 8 days	Visit 4 + 30 days
Time windows (days)	-		+14 days		+14 days				+21 days
Informed consent	X								
Inclusion/exclusion criteria	X								
Collection of demographic data	X								
Medical history (including maternal prenatal pertussis vaccination)	X								
Physical examination§	X						X**		
Measurement of temperature††	X		X		X		X		
Contact IRT system for randomization, allocation of subject number, and vaccine assignment	X								
Contact IRT system for vaccine assignment			X		X		X		
Review of temporary contraindications for blood sampling‡‡			X		X				X
Blood sampling (BL)§§			BL1 (3 mL)		BL2 (3 mL)		BL2 (3 mL)***		BL3 (6 mL)
Review of warning and precautions to vaccinations	X		X		X		X		
Review of contraindications to subsequent vaccinations and conditions for withdrawal†††			X		X		X		
Vaccination with Bexsero®	X				X		X		
Vaccination with routine pediatric vaccines‡‡‡	X		X		X				
Immediate surveillance (30 minutes) and recording of any immediate unsolicited AEs	X		X		X		X		
Diary card (DC) provided§§§	DC		DC		DC		DC		

Visit	Visit 1	Telephone Call (TC) 1*	Visit 2	TC2*	Visit 3	TC3*	Visit 4†	TC4*	Visit 5‡
Approximate age of subjects	2 months	-	3 months	-	4 months		12-13 months	-	13-14 months
Trial timelines (days)	Day 0	Visit 1 + 8 days	Visit 1 + 30 days	Visit 2 + 8 days	Visit 2 + 30 days	Visit 3 + 8 days	-	Visit 4 + 8 days	Visit 4 + 30 days
Time windows (days)	-		+14 days		+14 days				+21 days
Telephone call		X		X		X		X	
Diary card reviewed and collected			DC		DC		DC		DC
Recording of solicited injection site & systemic reactions	X		X		X		X		
Recording of unsolicited AEs	From Day0 to Day30 after each vaccination								
Reporting of serious adverse events (SAEs, including AESIs)****	To be reported throughout the trial								
Collection of reportable concomitant medications	X		X		X		X		X
Trial termination record									X

Note: Each visit may be conducted at the site (site visit) or at the subject's home (home visit).

* This call is made 8 days after the respective vaccinations. If day 8 falls on a weekend or holiday, the telephone call may be made on the following business day. During this telephone call, the staff will find out whether the subject experienced any SAE not yet reported and will remind the subject's parent / legally acceptable representative to continue using the diary card, and confirm the date and time of the next visit.

† Visit 4 may occur anytime from the day the subject becomes 12 months of age until the day before becoming 14 months of age.

‡ Routine pediatric vaccines may be given as per standard of care outside of the study, after all visit procedures have been completed.

§ Physical examination should be performed as per standard of care.

**A health assessment will be performed by a study nurse at Visit 4. A physical examination may be performed on the basis of relevant medical history/study nurse health assessment according to the investigator's clinical judgment.

†† Temperature (route as per standard of care) needs to be measured before each vaccination and recorded in the source documents.

‡‡ Should a subject receive oral or injectable antibiotic therapy within 3 days prior to any blood draw, the investigator will postpone that blood draw until it has been 3 days since the subject last received oral or injectable antibiotic therapy. Postponement must still be within the timeframe for blood draw. If postponement would result in the sample collection falling outside of this timeframe, the blood sample should be collected without postponement, and it should be documented appropriately that the sample was taken less than 3 days after stopping antibiotic treatment.

§§ Blood sample will be drawn prior to vaccination.

*** Blood samples will be drawn from ~ 70 randomized subjects only (Subset A).

††† Blood samples will be drawn from ~ 90 randomized subjects only (Subset B).

‡‡‡ A physical examination may be performed on the basis of relevant medical history at the time of the visit according to the investigator's clinical judgment.

§§§ Routine pediatric vaccines: At Visit 1: Infanrix hexa®, Rotarix®, Prevenar 13®; at Visit 2: Infanrix hexa®, Rotarix®; at Visit 3: Infanrix hexa®, Prevenar 13®. Licensed ACWY conjugate meningococcal vaccine (Nimenrix®) will be offered 30 days after the last study visit (Visit 5) at an additional optional visit.

**** The diary card dispensed to the subject's parent/legally acceptable representative at each visit must correspond to the number of injections given at that visit.

†††† AESIs will be collected throughout the trial as SAEs to ensure that the events are communicated to the Sponsor in an expedited manner and followed up until the end of the follow-up period or resolution, as per the assigned causality.

List of Abbreviations

µg	microgram
AE	adverse event
AESI	adverse event of special interest
AR	adverse reaction
BL	blood sampling
CDM	Clinical Data Management
CQA	Clinical Quality Assessment
CRA	Clinical Research Associate
CRB	(electronic) case report book [all the case report forms for a subject]
CRF	(electronic) case report form
CTA	clinical trial agreement
CTL	Clinical Team Leader
EDC	electronic data capture
FAS	full analysis set
FVFS	first visit, first subject
FVLS	first visit, last subject
GCI	Global Clinical Immunology
GCP	Good Clinical Practice
GMT	geometric mean titers
GPV	Global Pharmacovigilance
IATA	International Air Transport Association
ICF	informed consent form
ICH	International Council for Harmonisation
IDMC	Independent Data Monitoring Committee
IEC	Independent Ethics Committee
IM	intramuscular
IME	important medical event
IRB	Institutional Review Board
IRT	interactive response technology
LCLS	last contact, last subject
LLOQ	lower limit of quantitation
LLT	lowest level term
MedDRA	Medical Dictionary for Regulatory Activities
mL	milliliter

NIMP	non-investigational medicinal products
NSAID	non-steroidal anti-inflammatory drug
PPAS	per-protocol analysis set
PRN	pertactin
PRP	polyribosyl-ribitol phosphate
PS	polysaccharide
PV	Pharmacovigilance
RCDC	reverse cumulative distribution curves
RMO	Responsible Medical Officer
RV	rotavirus vaccine
SAE	serious adverse event
SafAS	safety analysis set
SAP	statistical analysis plan
SCID	severe combined immunodeficiency disorder
SOC	system organ class
SMT	Safety Management Team
TBD	to be determined
TC	telephone call
TMF	trial master file
UK	United Kingdom
US	United States

1 Introduction

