Note: Each visit may be conducted at the site (site visit) or at the subject's home (home visit).

Blood Sampling

Subjects will provide the following blood samples:

- Groups 1 and 2: 160 subjects in each group will be randomized to have 3 blood draws at the intervals mentioned below. The remaining subjects will only have 1 blood draw at Visit 5.
- Group 3: all 160 subjects will have 3 blood draws.

For the subjects randomized to have 3 blood draws in Group 1 and Group 2, the first 2 blood draws will be performed in a staggered way – approximately half of the subjects (~70 subjects in each group) will have blood draws at Visit 2 and Visit 3 (subset A), and the remaining half (~90 subjects in each group) will have blood draws at Visit 3 and Visit 4 (subset B). The third blood draw will be performed at Visit 5 for all subjects.

Subset A (~70 subjects in each group):

- a pre-vaccination blood sample at Visit 2
- a blood sample at Visit 3 (30 days after vaccination at Visit 2)
- a blood sample at Visit 5 (30 days after vaccination at Visit 4)

Subset B (~90 subjects in each group):

- a blood sample at Visit 3 (30 days after vaccination at Visit 2)
- a pre-vaccination blood sample at Visit 4
- a blood sample at Visit 5 (30 days after vaccination at Visit 4)

For the subjects randomized to Group 3, the first 2 blood draws will be performed in a staggered way – approximately half of the subjects (~70 subjects) will have blood draws at Visit 2 and Visit 3 (subset A), and the remaining half (~90 subjects) will have blood draws at Visit 3 and Visit 4 (subset B). The third blood draw will be performed at Visit 5 for all subjects.

Subset A (~70 subjects):

- a pre-vaccination blood sample at Visit 2
- a blood sample at Visit 3 (30 days after vaccination at Visit 2)
- a blood sample at Visit 5 (30 days after vaccination at Visit 4)

Subset B (~90 subjects):

- a blood sample at Visit 3 (30 days after vaccination at Visit 2)
- a pre-vaccination blood sample at Visit 4
- a blood sample at Visit 5 (30 days after vaccination at Visit 4)

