- 12) Remind the parent / legally acceptable representative to expect a telephone call 8 days after Visit 1.
- 13) Remind the parent / legally acceptable representative to notify the site in case of an SAE.
- 14) Complete the relevant case report forms (CRFs) for this visit.

Telephone Call 1 (8 days after Visit 1)

Note: If day 8 falls on a weekend or a holiday, the telephone call may be made on the following business day.

- 1) Record relevant information concerning the subject's health status on the telephone contact form. If an SAE, including an AESI occurred, follow the instructions in [Section 10](#) for reporting it.
- 2) Remind the parent / legally acceptable representative to do the following:
 - Complete the D0 to D07 pages of the diary card.
 - Complete the remaining pages of the diary card.
 - Notify the site in case of an SAE.

Visit 2 (30 [+14] days after Visit 1): Collection of Safety Information, Vaccination, and Blood Sample

- 1) Collect and review the diary card with the parent / legally acceptable representative, including any AEs, medications, or therapy that occurred since vaccination. If an SAE, including an AESI, has occurred, follow the instructions in [Section 10](#) for reporting it.
- 2) Measure temperature. If the temperature is $\geq 38^{\circ}\text{C}$, postpone vaccination until the condition is resolved.
- 3) Review temporary contraindications for blood sampling. Ensure the subject has not had any antibiotics within the previous 72 hours (3 days).
- 4) Collect 3 mL of blood from the subjects in Subset A (BL1) (see [Section 5.1.2](#) and [Section 5.1.3](#) for definition of Subset A and details of the sample schedule, and [Section 7.1](#) for detailed instructions regarding the handling of blood samples). All attempts should be made to obtain a blood sample; however, if the attempts are unsuccessful, the subject could continue in the study with all the study procedures including vaccination.
- 5) Review warnings and precautions to vaccinations.
- 6) Review contraindications to subsequent vaccinations and conditions for withdrawal.
- 7) Contact the IRT system for vaccine assignment.
- 8) Administer the following vaccines. Each vaccine should be administered in the assigned location and documented appropriately.
 - MenACYW conjugate vaccine: inject IM into the anterolateral area of the thigh
 - Infanrix hexa[®]: inject deep IM into the anterolateral area of the thigh

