 - Bexsero[®]: inject deep IM into the anterolateral area of the thigh.
 - Infanrix hexa[®]: inject deep IM into the anterolateral area of the thigh
 - Prevenar 13[®]: inject IM into the anterolateral area of the thighIf multiple vaccines are administered at a single visit, each vaccine should be administered at a different anatomic site. If vaccines are given in the same limb, the injection sites should be separated by 1 inch or more, so that any local reactions can be differentiated.
- 9) Observe the subject for 30 minutes and record any AEs in the source document. In the event of a local reaction, indicate the associated vaccine.
- 10) Give the parent / legally acceptable representative a diary card (the diary card should match the number of injections given during this visit, 3 injections for all groups)
- 11) Remind the parent / legally acceptable representative to expect a telephone call 8 days after Visit 3.
- 12) Remind the parent / legally acceptable representative to notify the site in case of an SAE.
- 13) Complete the relevant CRFs for this visit.

Telephone Call 3 (8 days after Visit 3)

Refer to steps in Telephone Call 1.

Visit 4 (12 to 13 months): Collection of Safety Information, Vaccination

- 1) Collect and review the diary card with the parent / legally acceptable representative, including any AEs, medications, or therapy that occurred since vaccination. If an SAE, including an AESI, has occurred, follow the instructions in [Section 10](#) for reporting it.
- 2) A physical examination may be performed as per standard of care on the basis of relevant medical history/study nurse health assessment according to investigator's clinical judgment.
- 3) Measure temperature. If the temperature is $\geq 38^{\circ}\text{C}$, postpone vaccination until the condition is resolved.
- 4) Review temporary contraindications for blood sampling. Ensure the subject has not had any antibiotics within the previous 72 hours (3 days).
- 5) Collect 3 mL of blood from the subjects in Subset B (BL2) (see [Section 5.1.2](#) and [Section 5.1.3](#) for definition of Subset B and details of the sample schedule, and [Section 7.1](#) for detailed instructions regarding the handling of blood samples).
- 6) Review warnings and precautions to vaccinations.
- 7) Review contraindications to subsequent vaccinations and conditions for withdrawal.
- 8) Contact the IRT system for vaccine assignment.

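### The Group 3 procedures table contradicts the text on who is bled at Visits 2 and 4, and its footnote markers are one step out

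*Protocol*

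**What the plan says.** **The text.** The synopsis, Section 5.1.1 and Section 7 agree on Group 3. All subjects (160 planned) give three samples. About 70 (Subset A) are bled at Visits 2, 3 and 5. For the others, Section 5.1.1 states that "the remaining half (~90 subjects) will have blood draws at Visit 3 and Visit 4 (subset B", with a third sample at Visit 5. The steps in Section 5.1.4 match this. At Visit 2 the instruction is "Collect 3 mL of blood from the subjects in Subset A (BL1", at Visit 3 both subsets are named, and at Visit 4 it is "Collect 3 mL of blood from the subjects in Subset B (BL2". Table S1 limits the Group 3 draws at both Visit 2 and Visit 4 to a subset, and Table 5.1 gives n=70 at Visit 2.

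**The Group 3 procedures table.** Its heading announces "4 Telephone Calls, 3 Blood Samples, 11- to 12-Month Duration per Subject". The blood-sampling row shows:

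- Visit 2: BL1, no marker
- Visit 3: BL2, no marker
- Visit 4: BL2, marked `***`
- Visit 5: BL3

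The table's own note for `***` is "Blood samples will be drawn from ~ 70 randomized subjects only (Subset A". Its Subset B note, `†††`, is attached instead to the row "Review of contraindications to subsequent vaccinations and conditions for withdrawal". Section 7 names the procedures table, together with Section 5.1.3, as the place to find the sampling schedule.

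**The concern.** The table gives a different sampling plan from the rest of the protocol. A site working from it could bleed Subset B at Visit 2 and Subset A at Visit 4, neither of which is planned. It could also miss the planned Subset B sample taken before Bexsero at Visit 4.

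Two things would be at stake. The first is blood draws in infants that the plan does not call for. The second is the Group 3 Visit 4 data. FAS2 and PPAS2 (Sections 12.2.1.2 and 12.2.3.2) admit a subject only with a valid Visit 4 result, so the Group 3 members of those sets are meant to come from Subset B.

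The fallback is also imperfect. The visit steps send the reader to Sections 5.1.2 and 5.1.3 for the subset definitions, but Section 5.1.2 justifies the design and defines no subset.

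**Working it through.** **Inputs.** Subset A is about 70 and Subset B about 90 (Section 5.1.1). Volumes are 3 mL at Visits 2, 3 and 4 and 6 mL at Visit 5 (Section 7.1). Non-adherence is 30% (Section 12.5).

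**1. Reproduce the plan's figure.** 70 + 90 = 160 subjects. Draws by visit are 70 + 160 + 90 + 160 = 480, and 480 / 160 = 3 per subject. This matches the stated three draws for everyone in Group 3.

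**2. Count the table read literally.**

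| Visit | Text | Table, literal | Difference |
|---|---|---|---|
| 2 | 70 (A) | 160 (A and B) | +90, all Subset B |
| 3 | 160 | 160 | 0 |
| 4 | 90 (B) | 70 (A) | +70 Subset A, −90 Subset B |
| 5 | 160 | 160 | 0 |
| Total | 480 | 550 | +70 |

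Unplanned draws: 90 + 70 = 160. Planned draws omitted: 90. Net: 160 − 90 = 70, which equals 550 − 480.

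**3. Per infant.** Subset A: four draws, 3 + 3 + 3 + 6 = 15 mL, against three draws, 3 + 3 + 6 = 12 mL. Subset B: still three draws and 12 mL, but at Visits 2, 3 and 5 instead of 3, 4 and 5. The conflict with the heading's three samples therefore arises for Subset A only.

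**4. Visit 4 numbers.** If the 30% non-adherence applies evenly to the subsets (an assumption), evaluable Group 3 samples at Visit 4 would be 0.7 × 90 = 63 under the text and 0.7 × 70 = 49 under the table, from different infants.

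**5. Footnotes in the Group 3 table.**

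| Marker | Row that carries it | What its note is about |
|---|---|---|
| `***` | Blood draw, Visit 4 | Subset A, about 70 |
| `†††` | Contraindications to further vaccination | Subset B, about 90 |
| `‡‡‡` | Routine vaccines | Physical examination |
| `§§§` | Diary card provided | List of routine vaccines |
| `****` | SAE reporting | Diary card and number of injections |
| `††††` | None | AESIs collected as SAEs |

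For example, the note for `‡‡‡` begins "A physical examination may be performed on the basis of relevant medical history at the time of the visit", yet the marker stands on the routine-vaccine row. The row "Reporting of serious adverse events (SAEs, including AESIs" points to the diary-card note, while the AESI note has no anchor. From `†††` to `****` each marker is exactly one place behind the note its row needs.

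**6. Comparison with the other groups.** The Group 1 and Group 2 tables describe the same sampling design. They use `***` at Visit 2 and `†††` at Visit 4, in line with the text, and their later markers match their notes.

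**7. A separate small point.** In all three tables the row for temporary contraindications to blood sampling is blank at Visit 4, although Section 5.1.4, Visit 4 step 4, requires that check.

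**The case against.** The strongest reply is that this is an editorial slip corrected many times over. The right subsets stand in the synopsis, Sections 5.1.1 and 7, and the visit steps that staff follow. Section 7 spells out the correct Group 3 schedule immediately before it refers to the table. Section 7.1 requires a pre-printed label with subject number and sampling stage to be verified before each draw. The literal reading also looks wrong on its face: Subset A would give two samples both called BL2, and a blood-draw note would hang on a contraindications row. Most readers would see misnumbered notes. On this view the 550-draw count measures a scenario and not a defect in the planned data, and Group 3 immunogenicity is descriptive only.

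Most of that stands, and it limits the consequence. The counts are an outer bound. It does not make the table correct, because the table is an operational page that the protocol itself cites for sampling.

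A second reply is that the PDF conversion may have broken the table. That is possible for the missing Visit 2 marker and for the single BL2 label at Visit 3. It does not explain the `***` that is present at Visit 4, or a uniform one-step shift over four further rows. A note added to the list without re-marking the table body would explain both, though that is an inference.

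**Conclusion.** The Group 3 table contradicts the protocol's own text on which infants are bled at Visit 2 and Visit 4, and should be corrected. Read literally it implies 160 unplanned draws, 90 omitted Subset B draws at Visit 4, and a fourth sample for Subset A.

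Those figures rest on two assumptions: that the subsets are about 70 and 90, and that a site follows the table over the visit steps. The second is a risk and not an expectation.

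The exposure is confined to the observational Group 3 immunogenicity, for which Section 12.1.3 plans descriptive statistics and no hypothesis test. The primary Group 1 versus Group 2 comparison, its sample size and its power are untouched.

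**What to change.** Bring the Group 3 table into line with Sections 5.1.1, 5.1.4 and 7:

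- Mark the Visit 2 draw as Subset A and the Visit 4 draw as Subset B.
- At Visit 3, label the draw BL2 for Subset A and BL1 for Subset B, as in the Group 1 and Group 2 tables; all 160 are drawn.
- Move the four shifted row markers (`†††`, `‡‡‡`, `§§§`, `****`) so that each row points to its own note, and anchor the AESI note `††††` to the SAE row.
- In all three tables, reconcile the blank Visit 4 cell in the blood-sampling contraindications row with Section 5.1.4.

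With the first two changes the count returns to 70 + 160 + 90 + 160 = 480 draws, three per infant. The cost is a table correction in the next amendment and a short memo to sites, with no new data, subjects or analyses.
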